ORI IRB# 00000278

Protocol Version 9/1/2021

Official Title: Utilizing Smart Speaker Technology to Deliver Parenting Education Support to Parents of Young Children

Principal Investigators: [name].

Oregon Research Behavior Interventions Strategies, dba Influents Innovations

Award No. R43HD101190-01A1

Final Version Dated: 9/1/2021

STUDY PROTOCOL

Participant Recruitment, Enrollment, and Overall Design

Families were recruited to participate in the feasibility evaluation study via distribution of study information through parenting support agencies, Head Starts, childcare centers, and Women, Infants, and Children (WIC) offices. Interested parents who contacted project staff were provided additional information about the study and screened for eligibility; those eligible were sent the informed consent form. After signing the consent, primary parents completed the pretest (T1) assessment and then were sent an Echo Dot with the Bedtime Routine enabled. Parents were asked to engage with TP at least 8 times over 4 weeks; project staff provided prompts during the 4-week period to encourage usage and provide technical support as needed. At 4 weeks after T1, parents were administered the posttest (T2) questionnaire. This design allowed evaluation of T1-T2 change and satisfaction/usability of the TP Bedtime Routine prototype. Parents were given \$20 for completing the T1 assessment and 3 uses of TP, and \$20 for completing the T2 assessment. Those who used the TP program at least 8 times were entered into drawings for a \$50 gift card.

Talk Parenting (TP) Bedtime Routine

The Alexa-based Talk Parenting app prototype (called a “skill”) uses smart speaker technology to provide in-situ experiential support to families of 3-5-year-old children, for a positive bedtime routine that promotes children’s healthy sleep habits and a positive parent-child relationship. The TP prototype Bedtime Routine contains 14 bedtime steps supported with cues and reinforcements, 4 songs, 3 stories, 3 relaxation guides, and 3 choices for going-to-sleep music. Through simple voice activation, these media assets prompt parents and children through a series of interactive steps to create a positive, fun, and relationship-building bedtime routine. In addition, 4 podcast episodes provide advice to parents on the most common challenges of bedtime, such as managing bedtime resistance, calling out, and crying.

Measures

T1 and T2 questionnaires measured primary parents’ parenting practices (Program-Targeted Parenting Practices (PTPP) Frequency of Engagement and Satisfaction Handling Bedtime subscales (Cronbach’s alphas in present sample =.87 & .96); Parenting and Family Adjustment Scale (PAFAS) Coercive Parenting and Positive Encouragement subscales (alphas=.46 & .74)); self-efficacy (Self-Efficacy for Parenting Tasks Index (SEPTI) Discipline and Routine subscales (alphas=.89 & .87); PTPP Self-Efficacy subscale (alpha=.96)), and stress (Parental Stress Scale (PSS; alpha=.86)); children’s behavior (Child Adjustment and Parent Efficacy Scale (CAPES) Behavior Problems subscale (alpha=.76)), emotional adjustment (CAPES Emotional Adjustment subscale (alpha=.84)), and sleep problems (Short-Form Children Sleep Habits Questionnaire (SF-CSHQ; alpha=.72)); and the parent-child relationship (Child-Parent Relationship Scale (CPRS) Closeness and Parent-Child Conflict subscales (alpha=.80 & .74)). The T2 questionnaire also contained measures of parent satisfaction, acceptability, and usability of the Talk Parenting skill. Demographics were collected at T1. Usage data measured families’ usage of TP.

STATISTICAL ANALYSIS PLAN

The evaluation had three main goals: (a) establish the initial efficacy of the Talk Parenting Bedtime Routine; (b) determine the participants’ perceptions of usability, acceptability, and satisfaction regarding the TP Bedtime Routine; (c) and determine the amount of program use.

Paired t-tests were used to examine T1-T2 data to determine whether there were significant improvements in parenting and child outcomes after engaging with the TP Bedtime Routine skill. The point-biserial r provide the measure of effect size, with the convention of $.14=\text{small}$, $.36=\text{medium}$, and $.51=\text{large}$. Examination of descriptive statistics for the user satisfaction and acceptability items informed on participants' reactions to the program. A descriptive summary of the program usage data provides evaluation of families' use of the Bedtime Routine.

Due to the substantial missing data at posttest, change in parenting and child outcomes from pretest to posttest was evaluated only with participants who completed both the T1 and T2 assessments ($n= 17$). Failure to provide T2 data was minimally associated with T1 scores on outcome measures, indicating a low likelihood of bias when interpreting observed data only. A significant decrease in power was realized: With 17 dyads with both T1 and T2 data, the study is powered to detect significant change in outcomes associated with large effects ($r > .65$). Thus, in addition to statistical significance, we interpret medium or greater effects ($r > .35$) as initial evidence that parenting and child outcomes showed meaningful change after engaging with the Talk Parenting program.

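### Does sending the device after T1, with T2 fixed at 4 weeks after T1, leave the exposure and usage window too poorly defined?

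*Combined protocol and SAP*

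**What the plan says.** The section on recruitment, enrollment and overall design gives the order of events. After consent, "primary parents completed the pretest (T1) assessment and then were sent an Echo Dot with the Bedtime Routine enabled". The use request follows: "Parents were asked to engage with TP at least 8 times over 4 weeks". Staff support is described over the same length of time: "project staff provided prompts during the 4-week period to encourage usage". The next sentence sets the posttest: "At 4 weeks after T1, parents were administered the posttest (T2) questionnaire". The incentive rule is tied to a count and carries no dates: "Those who used the TP program at least 8 times were entered into drawings".

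The Statistical Analysis Plan lists amount of use as the third of three main goals and handles it descriptively: "A descriptive summary of the program usage data provides evaluation of" families' use of the routine. T1-T2 change is tested with paired t-tests. The final paragraph of the plan reads medium or larger effects as a first sign that outcomes "showed meaningful change after engaging with the Talk Parenting program".

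Neither part gives a dispatch, delivery, set-up or first-use date, a T2 window, or a cutoff for counting uses.

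**The concern.** The posttest is timed from T1, but the family cannot start until a device posted after T1 has arrived and been set up. The use period has a length and no written start. If it runs from T1, its first days pass without a device. If it runs from receipt, its last days fall after T2, and uses on those days cannot have contributed to T1-T2 change.

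Two things would be at stake. First, the usage result might be hard to set against the 8-use request, because a reader would not know over how many days uses were counted. Second, the T1-T2 results might be taken to reflect four full weeks with the program when the scheduled access was shorter.

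**Working it through.** The documents give no access figure to reproduce, so the check is date arithmetic plus a reading of the text.

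**Inputs from the documents.** T2 is 28 days after T1; the request is 8 uses over 4 weeks; the device is sent after T1.

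**Assumed input.** The delay *d* from T1 to a working device is not documented. I take 1, 3, 7 and 14 days for illustration only.

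**Formulas.**
- Access before T2 = 28 − *d*
- Share of 4 weeks lost = *d*/28
- Weekly rate needed for 8 uses before T2 = 8 / ((28 − *d*)/7); with *d* = 0 this is 8/4 = 2.00

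| Assumed delay (days) | Access before T2 (days) | Share lost | Uses a week needed for 8 |
|---|---|---|---|
| 1 | 27 | 3.6% | 2.07 |
| 3 | 25 | 10.7% | 2.24 |
| 7 | 21 | 25.0% | 2.67 |
| 14 | 14 | 50.0% | 4.00 |

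The share lost is the assumed delay divided by 28 and nothing more, so the 50% is the chosen upper bound restated.

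**Can the request still be met?** The skill is a bedtime routine, so one use a night is possible. At the longest delay shown, 14 nights remain for 8 uses. At one use a night, 8 uses fit before T2 for any delay up to 28 − 8 = 20 days. The pace of 2 a week is a derived average; the protocol asks for a minimum total.

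**Which window does the text imply?** The sentences stand in this order: a use request over 4 weeks, staff prompts during that period, T2 at 4 weeks after T1, and then the statement that the design supports evaluation of T1-T2 change. Read together, they describe one period bounded by T1 and T2. Receipt of the device is never named as a starting point, so the reading in which some uses fall after T2 has no support in the text.

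**Does any analysis use exposure time?** The plan has paired t-tests on T1 and T2 scores, an effect-size *r*, descriptive satisfaction items and a descriptive usage summary. It has no dose-response model, no analysis set defined by adherence and no uses-per-week estimate. None of the table's quantities enters the t-tests, the 17 complete pairs, the *r* > .65 power statement or the *r* > .35 interpretation rule.

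**What would re-timing T2 do?** Timing T2 from delivery makes the T1-T2 interval 28 + *d*, which is 29 to 42 days over the assumed range, and it would differ between families.

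**The case for a change.** The best case for acting is that amount of use is a main goal of a feasibility study, and a count with no stated window is hard to judge against the 8-use request. A family keeping exactly 2 uses a week from receipt would have 2 × 27/7 = 7.7 uses by T2 after a 1-day delay, and 2 × 14/7 = 4.0 after 14 days. It could therefore miss the target because of shipping alone. Accepting the T1-to-T2 reading settles the window but not the lost days. The satisfaction and usability items were also collected at T2, after the same unstated exposure. One added sentence would cost almost nothing.

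Part of this stands. Under the stated schedule, access before T2 was somewhat under 4 weeks, and a careful report would state the counting window and, if recorded, the time from T1 to delivery. The rest is weaker:

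- The count is a valid description of what families did, whatever the delay. It would be understated only if counting stopped at T2 or day 28, and no cutoff is stated.
- The plan speaks of change after engaging with the program and does not claim four full weeks of access. If benefit grows with use, shorter access would weaken an observed effect rather than inflate it.
- The remedies are no clear improvement. Re-timing T2 swaps a fixed interval for one that varies by family, in a pre-post design with no control group, and applies only to a further cohort that the documents do not mention. Counting access from dispatch includes days in transit. A flat statement that access was under 4 weeks assumes that T2 was completed on day 28, and actual completion dates are not given.

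**Conclusion.** No change to the plan is called for. The sequence does imply less than 28 days of scheduled access before T2, but the size of the shortfall is not documented and cannot be computed. The range of 27 to 14 days rests wholly on the assumed delay of 1 to 14 days. On the ordinary reading, the use period runs from T1 to T2, and the 8-use request stays reachable at every delay considered, given that a bedtime routine can be used nightly. Followed as written, the plan gives valid paired t-tests and a valid descriptive count of use, and no test, sample size or threshold depends on days of access. Fixing T2 from T1 is a fair trade-off because it keeps the interval the same for every family. The missing counting window is a detail that an analyst would supply when writing up the usage data.

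### The change analysis leaves out T1 scores already held for families lost at T2; a two-occasion model on all enrolled families would use them, for a modest gain

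*Combined protocol and SAP*

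**What the plan says.** The Statistical Analysis Plan gives initial efficacy as its first goal and names one method for it: "Paired t-tests were used to examine T1-T2 data". The Measures section lists 13 outcome scales. The plan's last paragraph then restricts the analysis. The reason is "Due to the substantial missing data at posttest", and the consequence is that "change in parenting and child outcomes from pretest to posttest was evaluated only with participants who completed both the T1 and T2 assessments", with n = 17. The same paragraph reports that "Failure to provide T2 data was minimally associated with T1 scores on outcome measures" and infers that bias is unlikely. It gives r > .65 as the effect that 17 pairs can detect, and treats r > .35 as initial evidence of meaningful change alongside statistical significance.

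Under Participant Recruitment, Enrollment, and Overall Design, "primary parents completed the pretest (T1) assessment and then were sent an Echo Dot with the Bedtime Routine enabled". T1 therefore precedes any exposure.

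The documents do not state the number enrolled, the T1–T2 correlation, the size of the association between loss and T1, or the alpha and power behind r > .65. They describe no model that uses all enrolled families and no sensitivity analysis for missing T2.

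**The concern.** Missing T2 data do not require dropping a family's T1 score. The T1 scores of the lost families are held; without them the association between loss and T1 could not have been examined. They carry information on mean change because T1 and T2 are correlated.

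Read as an estimate for all enrolled families, the completers' change is right only if the completers' T1 mean matches the enrolled mean. If completers happened to start worse, part of their improvement is regression to the mean; if they started better, change is understated. With no control arm, nothing offsets this. Because the plan also interprets r > .35 without requiring significance, errors in the point estimate matter in themselves.

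**Working it through.** **Inputs.** From the plan: 17 complete pairs ("With 17 dyads with both T1 and T2 data"), paired t-test with 16 df, r > .65 and r > .35. Assumed: N = 25 to 51 enrolled, rho .3 to .9, equal SDs at T1 and T2. The plan gives no formula for r; r = t/√(t² + df) is used.

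**1. The plan's own figure.** With n = 17 and two-sided alpha 0.05, the noncentral t gives a detectable r of .598 at 80% power, .624 at 85% and .654 at 90%. Power at r = .65 is 89.4%. The Fisher-z formula at 80% power and r = .65 gives n = 16.06, rounded up to 17. So .65 is reproducible, but only by supplying an alpha and power that the plan does not state.

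**2. The error term.** Let G be the completers' T1 mean minus the T1 mean of all enrolled, and b the T2-on-T1 slope. The two-occasion normal likelihood estimate is

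change(all) = change(completers) + (1 − b) × G.

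With equal SDs b equals rho, so the completers' change is off by (rho − 1) × G, whether G is systematic or due to chance. If D is the completer-minus-lost difference, G = D × (1 − 17/N). For N = 34 and D = 0.2 SD, G = 0.10 SD and the error is 0.05 SD at rho .5 and 0.03 SD at rho .7. For D = 0.5 SD it is 0.125 and 0.075 SD.

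**3. Scale against r = .35.** t = 0.35 × √16 / √(1 − 0.35²) = 1.49, and 1.49/√17 = 0.36 SDs of the difference. At rho .5 the SD of the difference is √(2 × 0.5) = 1, so the threshold is 0.36 SD. An error of 0.05 SD is 0.05/0.36 = 14% of it.

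**4. What the attrition check can exclude.** The 95% CI half-width for D is about 0.89, 0.70 and 0.60 SD at N = 25, 34 and 51. A moderate difference could pass unnoticed. Chance alone also produces gaps: under completely random loss, |G| ≥ 0.2 SD occurs on 14–31% of scales for N = 25 to 50. That is 13 × 0.14 ≈ 2 to 13 × 0.31 ≈ 4 of the 13.

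**5. Precision.** The large-sample SE ratio, model to paired, is √{[(1 + rho) + (1 − rho) × 17/N]/2}. At N = 34 it is 0.94 for rho .5 and 0.96 for rho .7; over N = 25 to 51 and rho .3 to .9 it runs from 0.88 to 0.99. The detectable r at 90% power and N = 34 moves only from .65 to about .63–.64.

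**6. Simulation, N = 34, rho .5, true change 0.3 SD** (8,000 runs per setting)

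| Loss at T2 | Paired: bias, RMSE | Model: bias, RMSE |
|---|---|---|
| Completely random | 0.00, 0.241 | 0.00, 0.230 |
| Mildly T1-related | −0.075, 0.252 | 0.00, 0.231 |
| More strongly T1-related | −0.171, 0.295 | 0.00, 0.243 |
| Related to the change itself | +0.347, 0.419 | +0.268, 0.353 |

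The drop in mean squared error is 1 − (0.230/0.241)² = 9% in the first row and 1 − (0.231/0.252)² = 16% in the second.

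**7. Range.** For N = 25 to 50 and rho .3 to .7, mean squared error falls about 2–20% when loss is unrelated to T1. With an ordinary logistic slope of 0.3 per SD of T1, G is 0.09–0.19 SD, the bias removed runs from 0.3 × 0.09 ≈ 0.03 to 0.7 × 0.19 ≈ 0.13 SD, and mean squared error falls about 4–32%. At rho .8 the gain is about 1–5%.

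The simulations used the closed-form likelihood estimate, not a REML fit with Kenward–Roger intervals.

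**The case against.** **The association with T1 is reported as minimal.** If it truly is, the error removed is small, and the model then corrects mainly chance imbalance. This limits the size of the point but does not dispose of it: no figure is attached, and step 4 shows how little such a check can rule out. A reader might infer that a gap of 0.2 SD between completers and all enrolled is likely. The documents do not support that. Such a gap needs D = 0.2/(1 − 17/N), which is 0.63, 0.40 or 0.30 SD at N = 25, 34 or 50, and that is hardly a mild imbalance.

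**The model cures only one mechanism.** Families may fail to return T2 because they stopped using the program or saw no benefit. In the last row of the table 0.268/0.347 = 77% of the bias survives. This stands in full.

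**The target is presumed.** The plan asks about change after engaging with the program and never names all enrolled families as its population. For the completers' own change the paired t-test is unbiased, and the restriction is openly disclosed. This also stands, so the target has to be named.

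**The plan reads its results through r.** A replacement that gives only a contrast and an interval would leave the r > .35 criterion without a basis. The fix must supply r.

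**This is a single-arm feasibility evaluation,** where a disclosed complete-pair analysis is defensible. Agreed; that bears on how much weight the point deserves.

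**Conclusion.** The point holds as a modest improvement. The lost families' T1 scores are available, are left out of the change estimate, and can be used at almost no cost. Under loss that depends at most on T1, the likelihood estimate was unbiased, and its mean squared error was no higher than that of the paired estimate in any setting tried (N = 25 to 50, rho .3 to .8). The gains in step 7 rest on an assumed N and rho, equal SDs, a linear T2-on-T1 relation and, for the larger figures, an assumed relation between loss and T1.

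A reader might infer that the 17-pair results are biased or invalid, or that the model would recover the lost power. The documents support neither. They report no T1 gap of any size, and the detectable effect hardly moves. Nor does the model make the result safe against loss linked to change or program use.

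**What to change.** Replace the completers-only rule in the last paragraph of the Statistical Analysis Plan with:

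> For each outcome, T1 and T2 scores of all enrolled families enter a repeated-measures model with time as fixed effect and an unstructured 2×2 covariance (REML, Kenward–Roger). The mean change in all enrolled families and its 95% CI come from the time contrast, and r = t/√(t² + df) from that contrast is read against the r > .35 criterion. The paired t-test on the 17 complete pairs is reported as a sensitivity analysis. The model assumes that missing T2 depends at most on T1; it does not remove bias from loss related to change or program use.

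State the number enrolled beside the 17.

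The cost is a few lines of code and text, with no new data. The downside is reliance on a model, with an interval that may be about 2% wider when T1 and T2 are highly correlated. If the T1 imbalances are tiny the two analyses will agree, and showing that is useful in itself.

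### Similar pretest scores do not support the plan's conclusion that the 17-completer change analysis is unlikely to be biased

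*Combined protocol and SAP*

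**What the plan says.** The Statistical Analysis Plan calls the missing posttest data substantial and says that "change in parenting and child outcomes from pretest to posttest was evaluated only with participants who completed both the T1 and T2 assessments", with n = 17. It then gives its reason for trusting that subset: "Failure to provide T2 data was minimally associated with T1 scores on outcome measures, indicating a low likelihood of bias". In the same paragraph it acknowledges the loss of power and treats effects of r > .35 as "initial evidence that parenting and child outcomes showed meaningful change after engaging with the Talk Parenting program".

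No estimate, interval or threshold is given for the weak association. The documents do not state how many were enrolled, why participants did not return, or any sensitivity analysis.

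Information on engagement was collected. Under Measures: "Usage data measured families’ usage of TP". Under Participant Recruitment, Enrollment, and Overall Design, the first payment was for "completing the T1 assessment and 3 uses of TP", and "Those who used the TP program at least 8 times were entered into drawings" for a gift card. No comparison of use between those who did and did not return at T2 is described, and the documents do not say whether usage was recorded for every non-completer.

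**The concern.** A T1 comparison addresses one mechanism, dropout linked to baseline level. The efficacy analysis concerns change. A family that found the skill unhelpful, or stopped using it, could fail to return whatever its T1 score, and the T1 comparison would not reveal that.

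The sentence matters because it is the plan's only assurance that dropout did not distort the reading of r > .35 as meaningful change. Initial efficacy is the first of the three evaluation goals. Disclosing n = 17 and reduced power warns the reader about precision, not about bias.

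**Working it through.** **The plan's own figures.** The low-bias statement has no number to reproduce. The only power figure, r > .65 with 17 pairs, is not disputed: a two-sided 5% paired t-test at 90% power gives r = .654, although the plan states neither alpha nor power.

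**Why T1 similarity is not enough.** Let D = T2 - T1 and let p be a participant's probability of returning at T2. The bias in the completers' mean change is

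Cov(D, p)/E(p) = [Cov(T2, p) - Cov(T1, p)]/E(p).

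The T1 comparison informs only Cov(T1, p). If that is zero, the bias equals Cov(T2, p)/E(p), which involves T2 scores that were never seen.

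**Inputs.** From the plan: 17 completers and the r > .35 mark. Assumed: enrolled N of 25, 30 or 40; zero true change; T1 SD of 1; T2 = .6 T1 + e with e of SD .8; logit(p) = a + ln(OR) z with OR 1.5 or 2 per SD of z, and a set so that the return rate is 17/N.

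**Reference value.** r = .35 corresponds to t = .35 × √16/√(1 - .35²) = 1.495 on 16 df. With no change and no selection, P(t > 1.495) = .077.

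**Chance that completers exceed r > .35, one outcome** (noncentral t, noncentrality = √17 × completer mean change / completer SD of change; N = 25, 30, 40):

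| Return depends on | OR | Bias (T1 SD) | Expected T1 gap (SD) | P(r > .35) |
|---|---|---|---|---|
| Response unrelated to T1 | 1.5 | .100, .135, .180 | 0 | .166, .209, .271 |
| Response unrelated to T1 | 2 | .162, .217, .288 | 0 | .249, .339, .466 |
| Change itself | 1.5 | .112, .151, .201 | .175 | .180, .231, .305 |
| Change itself | 2 | .181, .243, .322 | .28 | .281, .387, .536 |

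Worked cell (row 2, N = 40): completer mean .288 and SD .859 give noncentrality .288/.859 × √17 = 1.38 and P = .466. With selection reversed, P falls to between .030 and .002.

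**Could the T1 check have detected this?** In simulated samples with exactly 17 returners, an observed T1 gap under .3 SD occurs in 52-66% of samples without selection and 43-59% with selection on change. Given such a gap, P(r > .35) is 15-45% with selection, about 7% without, and 0.2-3% if selection is reversed. Cut-offs of .2 and .4 SD give 15-44% and 15-47%. The comparison is also imprecise: with 17 completers and 8, 13 or 23 non-completers, the 95% interval for the gap has half-width .89, .75 or .65 SD.

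**What non-completers could do to the result.** If completers show r = .35, then d = 1.495/√17 = .362. If non-completers changed by k times as much, then d over all enrolled = .362 × (17 + k(N - 17))/N. This is converted back by t = d√17 and r = t/√(t² + 16), holding the SD of change at the completers' value.

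| k | N = 25 | N = 30 | N = 40 |
|---|---|---|---|
| -0.5 | .191 | .130 | .051 |
| 0 | .246 | .207 | .157 |
| 0.5 | .299 | .281 | .257 |
| 1 | .350 | .350 | .350 |
| 1.5 | .398 | .414 | .434 |

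For k = 0 and N = 40: d = .362 × 17/40 = .154, t = .635, r = .157.

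**The case against.** This is an uncontrolled feasibility study that discloses n = 17, substantial missing data and lost power, and calls its evidence initial. The T1 check has some value, since it bears on dropout by baseline severity. No bias has been shown. All of that stands, but it tempers the efficacy reading rather than supporting the separate statement about bias.

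The illustration can also be called high for this study. It selects on one outcome and reports that same outcome, whereas Measures lists 13 outcome subscales. If return instead depends on average change over 13 outcomes (assumed inter-correlation .2-.4), the chance per outcome is 12-33%. Where at least 10 of the 13 T1 gaps are under .3 SD, it is about 11-27%, against 7-8% without selection. The pre-post correlation matters too. For selection on change, a correlation of .3 raises the expected T1 gap to .23-.37 SD and lowers the chance, given a gap under .3 SD, to about 13-39%. A correlation of .8 gives a gap of about .12-.20 SD and about 16-48%. These points reduce the upper figures; the inflation remains.

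Finally, similar use in the two groups would not exclude dropout related to response. That is correct: the usage comparison is informative but cannot restore the assurance.

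**Conclusion.** The concern holds. The plan claims a property of the completer analysis that its only evidence cannot establish. This follows from the algebra and needs none of the assumed values. How far completers could mislead does depend on them: for a single outcome with no true change, the 7.7% chance of passing r > .35 could plausibly double or rise several-fold, or fall close to zero, while T1 scores look alike. The upper figures apply only if dropout tracks that particular outcome. Neither the presence nor the direction of bias is shown. The fault is one stated inference, not the paired t-test, and it should be fixed.

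**What to change.** - Replace the low-bias clause with a statement that completers and non-completers had similar T1 scores, and that bias from dropout related to response or engagement cannot be excluded.
- State the number enrolled.
- Where usage was recorded for non-completers, compare use by T2 status.
- Beside the paired t-tests, report a sensitivity analysis over assumed non-completer changes in both directions, as in the last table above. Zero change is one scenario, not a pass mark.
- Describe the r > .35 reading as applying to completers.
- Secondary: "The T2 questionnaire also contained measures of parent satisfaction, acceptability, and usability of the Talk Parenting skill", so report those results with the number of respondents out of the number enrolled.

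The cost is one reworded sentence, one number and a short extra analysis, with no new data. The usage comparison adds little work if the records exist and is not possible if they do not. The price is a less favourable statement of the evidence.

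### Does the stated sensitivity of 17 pairs (r > .65) conflict with the plan's own benchmark of .51 for a large effect?

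*Combined protocol and SAP*

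**What the plan says.** The relevant text is in the Statistical Analysis Plan section.

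- **Test:** "Paired t-tests were used to examine T1-T2 data".
- **Effect size:** "The point-biserial r provide the measure of effect size". The benchmarks are .14 for small, .36 for medium and .51 for large. No formula for r is given.
- **Sensitivity** (the paragraph on missing posttest data): the analysed number is 17, and on that basis the plan claims that "the study is powered to detect significant change in outcomes associated with large effects ($r > .65". No power level, alpha or sidedness is stated.
- **Interpretation** (the next sentence, offered as a consequence): "we interpret medium or greater effects ($r > .35$) as initial evidence". This reading is to apply alongside the tests, as the plan's phrase "in addition to statistical significance" shows.

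**The concern.** Three things catch the eye.

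1. The plan sets large at .51, then ties adequate power for large effects to .65. A reader who carries the first definition forward would think any effect of .51 or more is well covered, when power there is only a little over 60%.
2. At the conventional 80% power the detectable effect is about r = .59, so .65 looks like a miscalculation.
3. With 17 pairs, an observed r of about .47 already reaches two-sided significance. If .65 is read as the point below which nothing can be shown, the step to accepting r > .35 seems to rest on a false premise.

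If these points held, the study's sensitivity would be misreported, and the reason given for looking beyond significance would fail.

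**Working it through.** **Inputs from the plan:** n = 17 pairs, so df = 16; a paired t-test; benchmarks .36 and .51; stated detectable effect .65; interpretation threshold .35.

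**Assumptions, because the plan is silent:** two-sided alpha .05, and r = t/√(t² + df), the usual conversion for a paired t.

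**Formula.** Power comes from the noncentral t distribution with 16 df and critical t = 2.120. The noncentrality is δ = [r/√(1 − r²)] × √17 if r is taken from the standardised mean difference, or × √16 if it is taken from t and df. Both are shown.

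**The plan's own figure first.** At r = .65, r/√(1 − r²) = .65/√(1 − .4225) = .855. This gives δ = .855 × 4.123 = 3.53, or .855 × 4 = 3.42, and power of 91.1% or 89.4%. Working the other way, 90% power needs a standardised mean difference d_z = .838:

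- r = .838/√(1 + .838²) = .642
- by the other conversion, δ = .838 × 4.123 = 3.455 and r = 3.455/√(3.455² + 16) = .654

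The plan's .65 lies between these two values. Under the first conversion, 17 is also exactly the number of pairs needed for 90% power at r = .65.

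**Other points on the scale:**

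| True r | δ (√17 / √16) | Power |
|---|---|---|
| .35 | 1.54 / 1.49 | 30.5% / 29.0% |
| .36 (medium) | 1.59 / 1.54 | 32.2% / 30.6% |
| .51 (large) | 2.44 / 2.37 | 63.2% / 60.6% |
| .65 (stated) | 3.53 / 3.42 | 91.1% / 89.4% |

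**80% power.** d_z = .724 gives r = .724/√(1 + .724²) = .586, or .598 by the other conversion.

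**Smallest significant observed r.** 2.120/√(2.120² + 16) = .468. Power at a true r of .47 is 54.1% or 51.7%. A critical value marks roughly even odds of significance, and it always lies below the effect detectable at 80% or 90% power. So .468 and .65 answer different questions and do not compete.

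**Sensitivity to the assumptions.** With a one-sided .05 test, power at .65 is 95% to 96%. With a Fisher z calculation for a correlation, two-sided, it is 83%. It falls below 80% at a two-sided alpha of .01 (69% to 72%), but nothing in the plan points to that level.

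**The other reading of r.** If r is taken as the correlation of score with time point, then r = d/√(d² + 4) with d = .724 × √(2(1 − ρ)). That gives 80% power at r = .394, .340 and .270 for pre-post correlations ρ of .3, .5 and .7. The documents give no such correlation, and this is a two-group conversion applied to a paired test. The plan's .65 reproduces under the paired conversion, which is good reason to think that is the one intended.

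**The case for a change.** The strongest case for acting is this. The plan defined its own word, large, and then used it beside a different number without saying that effects from .51 to .65 are also large but less well covered. At .51 the study would miss nearly four true effects in ten, and 25 pairs would be needed for 80% power. Without power and alpha the figure cannot be checked uniquely: about .65 also fits one-sided .05 at 95% power and one-sided .01 at 80%. The figure also introduces the rule that admits r > .35. At 17 pairs an observed r of .35 gives t = .374 × 4 = 1.49 and p of about .15. Low power makes such a result inconclusive; it does not make it evidence.

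Part of this stands. Power, alpha, sidedness and the conversion to r are unstated, and large is loose wording for the upper part of the large range.

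The rest does not carry. The bracket is part of the sentence, and within it the claim is true. Testing the sentence at .51 tests something it does not say. Nor does the plan say that effects below .65 cannot be significant. The step to reading effect sizes alongside significance needs only that medium effects have low power. They do, at about 31% to 32% for .36, whether the detectable effect is quoted as .59 or .65. Whether r > .35 is a sound evidence rule is a fair question, but a separate one that correcting this sentence would not settle.

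**Conclusion.** The concern does not hold. The stated .65 is correct at about 90% power for a two-sided .05 paired t-test with 17 pairs, and it is consistent with a scale on which large begins at .51. It is also the more cautious of the two usual choices, since 80% power would have allowed the plan to quote about .59 to .60.

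The remaining gap is one of reporting. An analyst who assumes the standard settings recovers the figure to within .01, and sees from the two numbers that the stretch from .51 to .65 (power rising from about 61% to about 90%) lies outside the claim. The sentence describes sensitivity after attrition in a feasibility evaluation. It set no sample size and governs no test, estimate or cut-off, so rewording it would change nothing that is analysed or concluded.

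This rests on the assumed two-sided alpha of .05 with no multiplicity adjustment (the plan mentions none) and on r being derived from the paired t.
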